#### 3.2 Informed Consent Process

All participants must be provided a consent form describing the study with sufficient information for participants to make an informed decision regarding their participation. Participants must sign the IRB-approved informed consent prior to participation in any study-specific procedure. The participant must receive a copy of the signed and dated consent document. The original signed copy of the consent document must be retained in the subject's research file.

#### 3.3 Randomization Procedures

This study does not have randomization. All subjects must at least have one cutaneous SCC lesion and will apply topical remetinostat to SCC(s). If the subject has more than one SCC, a body map will remind subjects where to apply gel.

# 3.4 Study Timeline

#### **Primary Completion:**

The study will reach primary completion 18 months from the time the study opens to accrual. Individual subjects will reach primary completion 8 weeks after starting topical remetinostat treatment.

#### **Study Completion:**

The study will reach study completion 24 months from the time the study opens to accrual, e.g., allowing 6 months from Primary Completion for data analysis. Individual subjects will complete the study about 14 to 18 weeks after starting topical remetinostat treatment (e.g., Screening; 8 weeks treatment; post-treatment visit and surgical excision at Week 10 to 14, 4 weeks follow-up).

#### 4. TREATMENT PLAN

Adult subjects in the clinic who have one or more biopsy-proven cutaneous SCC or SCC-in situ (hereafter referred to as "SCC") lesions greater than or equal to 5 mm in diameter, at least one of which is being biopsied as a normal course of care, will be invited to participate in this trial. Eligibility of prospective participants will be confirmed, and subjects will enroll according to stated inclusion and exclusion criteria.

Screening visits may be combined with or without day 1 visit.

Prospective participants must be willing to sign a consent form. Subjects will also give consent to donate their SCC tissue for biomarker measurement and apply medication 3-times daily under bandage occlusion for 8 weeks. The anticipated bandage will be an adhesive bandage (e.g., "Band-Aid") with a non-adherent dressing, or paper tape with a non-adherent dressing.

Drug treatment: Subjects will be instructed to apply topical remetinostat to individual SCCs 3-times daily (TID) for 8 weeks. Patients will be asked to discontinue application of the medication at 8 weeks, approximately 2 weeks prior to their surgical excision(s), as dermal irritation from study drug may interfere with lesion identification at excision.

At least 1 target SCC will be identified requiring surgical excision per standard of care. In addition to being measured and photographed, this lesion(s) may be biopsied. Week 8 biopsy may be collected at the time of surgical excision of lesion(s). Histopathological evaluation of the specimen may be performed.

After an initial treatment application demonstration by the study team, treatment applications will be self-administered by the subject or a caregiver. Patients will receive oral and written administration instructions at the outset of the trial as follows:

"Study medication is to be applied to dry skin. Apply the study medication to the SCC lesion(s) designated by your physician, 3 times daily for 8 weeks, using clean washed finger(s)/ hand as applicable. Cover the treated SCC lesions(s) with a sticky strip bandage, such as a Band-Aid. If you start to treat new lesions or stop treating any lesion, please inform your physician so a record can be kept of which lesions are being treated with study medication. There is no need to leave large amounts of residue on your skin. If someone else helps apply the study medication, they should follow the same instructions. Immediately following application, wipe the finger(s) and hands you have used to apply the study drug with a disposable tissue and wash your hands using soap and water. If the study medication gets on the skin of other people, they should wash with soap and water. Alternatively, you or a caregiver can wear disposable gloves to apply the study medication, which will be supplied to subject on request."

Diary: after an initial explanation by the study team at the first visit, patients will be requested to fill out a medication diary to document application of the study drug (see Appendix A.) Patients will be requested to fill this out daily and requested to bring their diary with them to each study visit for review by the study team.

Tumors to be treated will be clearly identified. Patients will be instructed to store research medication in a refrigerator (see Appendix B). Patients will be offered a small portable medication cooler to utilize to keep their study drug cold.

All tumors will be measured and photographed at baseline, 4 weeks and after applying remetinostat for 8 weeks (at the Week 10 visit).

Paper case report forms will be used to capture source data for this study. A physician note will also be entered into Stanford's electronic medical record system for each of the study visits.

Patients may be contacted periodically to check on compliance and to follow up on AEs. Additional clinic visit(s) may be scheduled to assess AEs.

Given the absence of any remetinostat treatment related systemic AEs, together with the lack of effect on laboratory parameters or EKG, the minimal levels of remetinostat detected systemically reported in clinical studies to date, and the small BSA (< 0.5%) that will be treated with remetinostat gel, no lab assessments will be performed with the exception of a serum pregnancy test for women of child-bearing potential at baseline to assess eligibility for enrollment.

It is anticipated that the entire target tumor(s) will be surgically removed after the 8th week of treatment, in accordance with regular medical care; it is estimated that the surgical excision will occur between Weeks 10 to 14, depending on surgeon availability. A dose of remetinostat will be applied to the SCC by study personnel in clinic 30 mins before surgical excision. If surgical excision is delayed, i.e., does not occur at Week 10, remetinostat application may be continued for up to 4 additional weeks until surgical excision.

A follow-up visit will occur between Weeks 12 to 18 (approximately 2 to 4 weeks after Mohs/surgical excision), which may be in conjunction with surgery or a surgical follow-up visit,

or the visit may be conducted by phone. Patients may be contacted after completion of the study for additional follow up if deemed necessary by the Study Doctor.

SCC tissue biopsies will be collected from those who consent at baseline and Week 10 to evaluate the tumors treated with topical remetinostat gel 1%. The SCC biopsy will be collected in RNA later.

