# 7.2 Adverse Event Reporting

For guidance on reporting adverse events, refer to the Stanford Cancer Institute Clinical Trials Office Adverse Event SOP.

Adverse events will be graded according to CTCAE v5.0. Both Serious and Non-Serious Adverse Events will be clearly noted in source documentation and listed on study specific Case Report Forms (CRFs). The Protocol Director (PD) or designee will assess each Adverse Event (AE) to determine whether it is unexpected according to the Investigator's Brochure and/or protocol and related to the a) study drug or b) the investigation. All Serious Adverse Events (SAEs) will be tracked until resolution or until 30 days after the last dose of the study treatment.

All AE and SAEs will be reported to the Principal Investigator. The Stanford Cancer Institute Data and Safety Monitoring Committee (DSMC) will be informed of all SAEs. An AE is any unfavorable and unintended sign, symptom, or disease temporally associated with the use of an investigational medicinal product (IMP) or other protocol-imposed intervention, in this study topical remetinostat, regardless of attribution. This includes the following: AEs not previously observed in the subject that emerge during the protocol specified AE reporting period, complications that occur as a result of protocol-mandated interventions (e.g., invasive procedures such as biopsies); and preexisting medical conditions judged by the investigator to have worsened in severity or frequency or changed in character during the protocol-specified AE reporting period.

SAEs CTCAE Grade 3 and above, and all subsequent follow-up reports will be reported to the Stanford Cancer Institute Data and Safety Monitoring Committee (DSMC) using the study-specific CRF regardless of the event's relatedness to the investigation. Following review by the DSMC, events meeting the IRB definition of 'Unanticipated Problem' will be reported to the IRB using eProtocol within 10 working days of DSMC review, or within 5 working days for deaths or life-threatening experiences.

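### The 10-week timeframe for the safety outcomes ends before delayed application and follow-up do, and no scheduled contact is sure to reach 30 days after a pre-excision last dose

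*Combined protocol and SAP*

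**What the plan says.** All references are to the combined protocol and SAP.

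- **Safety outcomes.** Sections 10.2.1 to 10.2.4 (AEs, SAEs, AE-related discontinuation or interruption, and treatment compliance) each carry a timeframe of at most 10 weeks. Each is reported as a number of participants.
- **Excision.** Section 4 estimates that "the surgical excision will occur between Weeks 10 to 14, depending on surgeon availability".
- **Application near excision.** The same section states: "A dose of remetinostat will be applied to the SCC by study personnel in clinic 30 mins before surgical excision". If excision does not take place at Week 10, application may go on for up to 4 more weeks. The footnote to the Section 9 calendar caps the total at 12 weeks.
- **Follow-up.** Section 4 places one visit at Weeks 12 to 18, "approximately 2 to 4 weeks after Mohs/surgical excision". It may be by phone, and the text adds "which may be in conjunction with surgery or a surgical follow-up visit". Section 3.4 describes the end of participation as "post-treatment visit and surgical excision at Week 10 to 14, 4 weeks follow-up". Any contact after that is at the Study Doctor's discretion.
- **SAE rule.** Section 7.2 says that all SAEs "will be tracked until resolution or until 30 days after the last dose of the study treatment".
- **Competing statements on the last application.** An earlier paragraph of Section 4 has patients stop at Week 8, about 2 weeks before excision. Section 6.1 lets treatment stop about 2 weeks before excision if irritation could hide the lesion.

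**The concern.** Safety is the only secondary objective, and its outcomes are simple counts of participants. A count that closes at Week 10 excludes whatever happens at or after a later excision, during delayed application, and up to the Week 12 to 18 visit, although the schema gives safety monitoring as the purpose of that visit. Omitted events can only lower the counts.

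The second mismatch concerns collection of the data. If the last dose is the one given on the day of excision, the 30 days in Section 7.2 end after the last scheduled contact. Section 4.2 terminates the trial on an SAE related to the intervention, so the period over which SAEs are sought also bears on a trial-level rule.

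**Working it through.** **1. The plan's own figures.** Section 4: excision at Weeks 10 to 14 plus 2 to 4 weeks gives 10 + 2 = 12 and 14 + 4 = 18, the stated Weeks 12 to 18. Section 3.4: 10 + 4 = 14 and 14 + 4 = 18, the stated 14 to 18 weeks. Both reproduce. They differ at the early end, where Section 4 allows 2 weeks of follow-up and Section 3.4 gives 4.

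**2. The 10-week timeframe.** Assume that it runs from the first application.

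- Follow-up outside it: 12 − 10 = 2 weeks to 18 − 10 = 8 weeks.
- Delayed application outside it: 12 − 10 = 2 weeks if 12 weeks run without a break; 14 − 10 = 4 weeks if it continues up to a Week 14 excision.
- The pre-excision application falls between the last day of the timeframe (Week 10) and 4 weeks past it (Week 14).

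**3. The 30-day rule, if the pre-excision application is the last dose.** The 30 days close on day 7 × (excision week) + 30.

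| Excision | 30 days close on | Gap, contact at 2 weeks | Gap, contact at 4 weeks | Days after excision at end of Week 18 limit |
|---|---|---|---|---|
| Week 10 | day 100 (Week 14.3) | 30 − 14 = 16 days | 30 − 28 = 2 days | 56 |
| Week 12 | day 114 (Week 16.3) | 16 days | 2 days | 42 |
| Week 13 | day 121 (Week 17.3) | 16 days | 2 days | 35 |
| Week 14 | day 128 (Week 18.3) | 16 days | 2 days | 28 |

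Taken alone, the Week 18 limit would allow a contact at day 30 for excisions up to day 126 − 30 = 96 (Week 13.7). Nothing requires one. For a Week 14 excision the limit stops at day 28.

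**4. The same rule, if Week 8 is the last application.** The 30 days close on day 56 + 30 = 86 (Week 12.3). A contact at Week 12 (day 84) is 2 days short; contacts from day 86 on cover the window.

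**5. How many SAEs this could involve.** The documents give no SAE rate for this population. As an assumption, take the earlier 60-patient CTCL study (Section 7.1): 2 unrelated SAEs over 6 to 12 months of treatment, ignoring dropout.

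- Rate: 2/60 per 1 year = 0.033 to 2/60 per 0.5 year = 0.067 per person-year.
- With 40 subjects: 1.33 to 2.67 SAEs per year.
- Missed in a 2 to 16 day gap: 1.33 × 2/365 = 0.01 to 2.67 × 16/365 = 0.12 in the whole trial.
- Falling between Week 10 and the follow-up visit: 1.33 × 14/365 = 0.05 if every visit is at Week 12, to 2.67 × 56/365 = 0.41 if every visit is at Week 18. The visit could pick these up, but they lie outside the 10.2 timeframe.

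No comparable rate is given for non-serious AEs, so none is computed.

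**The case against.** **The 10-week label may not govern the analysis.** Section 10 is headed as registry and directory text. Sections 10.2.1 to 10.2.3 also speak of monitoring throughout the study, and the safety analyses in Sections 12.4.1 and 12.5 have no 10-week cutoff. This stands as far as it goes: the label does not show that later events go unrecorded. It leaves two incompatible periods for the same counts, and the protocol does not say which applies.

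**The 30-day rule may concern follow-up of known events.** Section 7.2 says that SAEs are tracked. It refers separately to an AE reporting period that the available text does not define, and to an institutional SOP that is not part of the documents. Known events can also be followed through the unscheduled contacts that Section 4 permits. A reader might infer that the protocol promises 30 days of collection for new SAEs and then fails to deliver it. That reading is reasonable, but the text does not state it.

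**The gap may be about 2 days.** Section 3.4 gives 4 weeks of follow-up, and Section 4's range is approximate. A reader might present the shortfall as 16/30 = 53% of the window. That uses only the early end of one section, so it is an upper bound.

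**The last dose may be earlier.** The Week 8 stop in Section 4 would remove most of the gap (step 4). The pre-excision application is equally explicit, so the conflict makes the size of the gap uncertain without settling it.

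**Follow-up on the day of surgery.** A reader might infer that the visit can coincide with excision, leaving no follow-up at all. The same sentence places it weeks after excision, so this is loose wording and not evidence of zero follow-up.

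**Few late related events are expected.** The documents report minimal systemic exposure and no treatment-related systemic AEs in the two CTCL studies. This limits the size of the problem. It does not remove the inconsistency, because the SAE outcome counts all SAEs whatever their cause.

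**Conclusion.** The point holds as a low-priority inconsistency in the safety reporting periods. The firmer part is the 10-week timeframe: followed as written, it leaves out delayed application and 2 to 8 weeks of follow-up that the protocol itself schedules. The second part is conditional. If the pre-excision application is the last dose, no mandatory contact reaches day 30. The shortfall is about 2 days at the late end and up to 16 at the early end, and for a Week 14 excision the Week 18 limit rules out day 30 altogether.

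A reader might go further and conclude that SAEs will be missed and the drug will look safer than it is. The documents do not support that. Under the borrowed rate, the 30-day gap accounts for about 0.01 to 0.12 SAEs in the whole trial, and the wording of Section 7.2 leaves open whether new SAEs were meant. The figures rest on counting the 10 weeks from first application and on 40 subjects with the earlier study's SAE rate. The primary ORR analysis is unaffected.

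**What to change.** 1. Set the timeframes in Sections 10.2.1 to 10.2.4 to run from first dose through 30 days after last dose, and refer to the same period in Sections 12.4.1 and 12.5.
2. Time the final safety contact at or after 30 days from the last application. Extend the Week 18 limit where needed; for a Week 14 excision on the last-dose reading in step 3, that means day 128 (Week 18.3). Align Section 3.4 and the Section 9 calendar.
3. State in Section 7.2 that the 30 days cover new SAEs as well as the follow-up of known ones, and define the AE reporting period.
4. Reconcile Sections 4, 6.1 and 9 on when the last application takes place, so that the 30 days have one starting point. Which statement is right is for the investigators to decide.

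The cost is moving or adding one phone call per subject, plus the text edits. The design, sample size and primary analysis do not change.

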#### 4.1 General Concomitant Medication and Supportive Care Guidelines

Concomitant therapy includes any prescription medications or over-the-counter preparations used by a subject between 1 month preceding the screening evaluation and the end of study visit.

Subjects who use oral contraceptives, hormone-replacement therapy, or other maintenance therapy will continue their use. All concomitant medications will be reported to the investigator and recorded on the appropriate CRF.

# 4.2 Criteria for Removal from Study

The trial will be terminated in the event of an SAE (Serious Adverse Event) related to the intervention. A Serious Adverse Event is any of the following:

- Fatal (i.e., the AE actually causes or leads to death).
- Life-threatening (i.e., the AE, in the view of the investigator, places the subject at immediate risk of death). It does not include an AE that, had it occurred in a more severe form, might have caused death (life-threatening does not include events such as blood values that do not by themselves represent an immediate risk of death).
- Requires or prolongs inpatient hospitalization.
- Results in persistent or significant disability/incapacity (i.e., the AE results in substantial disruption of the subject's ability to conduct normal life functions).
- Any occurrence considered by the investigator to be a significant medical event
   (e.g., may jeopardize the subject or may require medical/surgical intervention to prevent
   one of the medical outcomes listed above). All AEs that do not meet any of the criteria
   for serious should be regarded as non-serious AEs.

The investigator will use the following definitions to assess the relationship of the adverse event to the use of the study drug:

- **Probably-related**: An adverse event has a strong temporal relationship to the study drug or recurs on re-challenge and another etiology is unlikely or significantly less likely.
- Possibly-related: An adverse event has a strong temporal relationship to the study drug and an alternative etiology is equally or less likely compared the potential relationship to study drug.
- **Probably Not Related**: An adverse event has little or no temporal relationship to the study drug and/or a more likely alternative etiology exists.
- Not Related: An adverse even is due to an underlying or concurrent illness or effect of another drug and is not related to the study drug.

Subjects may be removed from the study because of subject wishes, non-compliance, or development of any medical condition that puts the subject at increased risk, in the opinion of the investigator.

The investigator has the right to discontinue a patient from study drug or withdraw a patient from the study at any time. In addition, patients have the right to voluntarily discontinue study drug or withdraw from the study at any time for any reason. Reasons for discontinuation of study drug or withdrawal from the study may include, but are not limited to, the following:

- Any subject who presents at screening or during treatment with a large (> 20 mm) SCC lesion: such a lesion will be discontinued from treatment (if applicable) and referred for evaluation for surgical resection. (If the patient has other, smaller lesions, these smaller lesions may be considered for enrollment in the study.)
- Subject withdrawal of consent at any time
- Any medical condition that the investigator or Sponsor determines may jeopardize the patient's safety if he or she continues in the study
- Investigator determines it is in the best interest of the patient
- Surgical or other treatment of target SCC before Week 8
- Pregnancy

#### 4.3 Alternatives

Alternatives to participation in the study include participating in a different clinical study, receiving medical care outside of a research study (including immediate surgical treatment), or no treatment.

#### 5. INVESTIGATIONAL DRUG INFORMATION

#### 5.1 Investigational Drug

Remetinostat is also known as suberohydroxamic acid phenyl ester (SHAPE); SHAPE Gel; SHP-141; and 4-[[8-(hydroxyamino)-1,8-dioxooctyl]oxy]-benzoic acid methyl ester. Remetinostat is a histone deacetylase inhibitor (HDACi) that was designed with a metabolically-labile ester bond so that topical application would produce effective local histone deacetylase (HDAC) inhibition in cutaneous lesions while resulting in only negligible systemic HDAC inhibition.

In this single-arm study, remetinostat is formulated at a strength of 1.0% in a gel consisting of dehydrated alcohol; propylene glycol; hexylene glycol; glycerin; oleyl alcohol; diisopropyl adipate; hydroxypropylcellulose; butylated hydroxytoluene and citric acid (anhydrous). The overall concentration of ethanol in the gel is approximately 50% (w/w). The primary packaging for remetinostat gel is aluminum tubes with plastic screw-on caps. The 60-g tubes are packaged in paper cartons (both labeled with identical labels).

See the remetinostat Investigator Brochure for additional information including the mechanism of action; summaries of animal and clinical studies; non-clinical and clinical pharmacokinetic; major route of elimination; safety profile; and the non-clinical and clinical data supporting the dose and regimen chosen for this study.

#### 5.2 Availability

Medivir AB is providing drug for this study.

#### 5.3 Agent Ordering

Remetinostat will be ordered by the Principal Investigator and shipped directly to the Stanford Dermatology Clinic, where it will be stored per manufacturer's guidelines and Stanford SOPs. Investigational drug will not be shipped to or held by Stanford Investigational Drug Services. The contact for drug ordering is:

Medivir AB [name] [contact]

E-mail: [contact]

#### 5.4 Storage Conditions

The Investigator is responsible for the control of the drug under investigation. The study agent will be kept in a locked refrigerator (2 to 8°C) in a secure area. Only trained research staff will have access to the locked refrigerator.

#### 5.5 Agent Accountability

Adequate records for the receipts (e.g., Drug Receipt Record) and disposition (eg, Drug Dispensing Log) of the study drug will be maintained. Accountability and subject compliance will be assessed by maintaining adequate "drug dispensing" and return records.

Accurate records must be kept for each study drug provided by the Sponsor. These records must contain the following information:

- Documentation of drug shipments received from the Sponsor (date received, quantity, and tube number)
- Disposition of unused study drug not dispensed to subject

A Drug Dispensing Log will be kept current and will contain the following information:

- The identification of the subject to whom the study medication was dispensed
- The date(s), quantity, and kit number of the study medication dispensed to the subject.
- The date(s), quantity and kit number of the study medication returned by the subject

Subjects will be asked to return all used and unused drug supply containers during and at the end of the treatment.

The investigational product will be returned to the Sponsor for disposal, or with the agreement of the drug manufacturer, destroyed in accordance with institutional SOPs.

